Adverse events from the OVA-301 trial, 1 dose-ranging randomized control trial, and 2 nonrandomized trials reported rates of grade 3 (severe) and 4 (life-threatening) adverse events of 89% vs 58% for trabectedin + PLD compared to PLD alone, respectively. The rates of discontinuation due to adverse events were 17% vs 9%, for patients who received trabectedin + PLD vs patients receiving PLD alone (Papaioannou et al, 2011). Adverse events from OVA-301 were collected from 333 patients receiving trabectedin + PLD and 330 patients receiving PLD alone. The most frequent grade 4 hematologic adverse events at least possibly related to treatment with trabectedin + PLD vs PLD included neutropenia (34% vs 8.5%), leukopenia (8.4% vs 2.4%), thrombocytopenia (8.1% vs 0.6%), anemia (3.0% vs 0.3%), and febrile neutropenia (2.4% vs 0.3%). The most frequent grade 4 nonhematologic adverse events that were more common with trabectedin + PLD therapy included increases in ALT (2.4% vs 0%) and AST (0.9% vs 0.3%). The most common adverse events leading to treatment termination or dose adjustment was neutropenia for trabectedin + PLD and hand-foot syndrome for PLD (Monk et al, 2010).

All patients must receive corticosteroids (e.g., 20 mg dexamethasone iv) 30 minutes prior to PLD (in combination therapy) or Yondelis (in monotherapy); not only as anti-emetic prophylaxis, but also because it appears to provide hepatoprotective effects. Additional anti-emetics may be administered as needed (Yondelis SmPC).

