4.3.1 Selection Criteria

Patients must comply with all of the following criteria in order to be enrolled into the study:

- Patients must be aged 18 years or older.
- Patients must have platinum-sensitive relapsed ovarian cancer, defined as disease relapse that occurs 6 months or more after completion of last platinum-containing therapy.
- Treatment indication according to local label SmPC and reimbursement for trabectedin and PLD treatment.
- Patients must have received a minimum of 1 cycle of trabectedin + PLD before their inclusion in the study.
- Patients must have signed an informed consent document indicating that they understand the
 purpose and procedures required for the study and are willing to participate in the study.

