6 STUDY PROCEDURES

This is a non-interventional study. Prior to the initiation of the qualification process or any study procedures, patients must sign an ICF indicating that they understand the purpose and procedures required for the study and that they are willing to participate in the study. The ICF must be signed 1 or more days following completion of the initial trabectedin + PLD administration (1st treatment cycle). The Study Schedule of Events is noted in Table 1 and Appendix 14.1, Figure 1.

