6.2 Observation Period

The Observation Period will begin with the first trabectedin + PLD dose administered after the signing of the ICF and will continue for up to a total of 12 months after that or until trabectedin treatment discontinuation, patient discontinuation for any reason or patient's death. PLD discontinuation is not a reason for Observation Period discontinuation. There are no predefined limits to the number of cycles administered. Trabectedin + PLD treatment can continue at the treating clinician's discretion.

Methods and timing of the imaging procedures will be determined by the treating clinician.

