5. DEFINITIONS

5.1 General

Study Day 1

Will be defined as-the first day with trabectedin + PLD administration therapy.

Baseline Tumor Imaging

The patient's baseline tumor imaging will be considered the imaging performed prior to the initial trabectedin + PLD administration (Day 1) or the earliest imaging study following Day 1.

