5.4 Safety

Adverse Events

All AEs (serious and non-serious, related and not related) reported from Day 1 of study treatment to 30 days post last dose of study treatment.

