6. ANALYSIS DATASETS

6.1 Full Analysis Set

The full analysis set (FAS) will consist of all the patients enrolled into the study and who have at least one administration of trabectedin. The FAS will be the primary analysis set for the safety analyses and analyses assessing effectiveness.

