9.5 Safety Analyses

9.5.1 Adverse Events

A solicited reporting system of AEs (serious and non-serious, related and not related) was used during this study, from the beginning of trabectedin + PLD treatment.

Whenever possible the investigator recorded the diagnosis, classified each adverse event in regards of seriousness and causal relationship to study drugs (trabectedin + PLD), and reported severity (grade).

AEs will be coded in the Medical Dictionary for Regulatory Activities (MedDRA) version 17.0 or higher by system organ class and a preferred term. Each event will be graded according to medical record documentation as 1 = mild, 2 = moderate, 3 = severe, 4 = disabling or life threatening consequences, and 5 = death.

The descriptive summaries presenting treatment emergent AEs will include AEs reported from Day 1 of study treatment to 30 days post last dose of study treatment. AE summaries will use the patient's maximum severity reported for each system organ class and preferred term. The corresponding summaries will be presented for AEs and SAEs grade 3 or higher.

Patient incidence of adverse drug reactions (ADR) related to trabectedin and related to PLD, respectively, will be tabulated by system organ class, preferred term and severity grade for all drug reactions and serious drug reactions. The corresponding summaries will be presented for ADRs and SADRs grade 3 or higher. ADR's relationship to treatment reported as unknown will be assumed to be related to both trabectedin and PLD.

In addition, and complementing the summaries above, AEs, SAEs, ADRs and SADRs will also be summarized by preferred term only, and in descending order of frequency.

A summary table will also be produced summarizing all event summaries and will include, AEs, SAEs, ADRs, SADRs, those leading to treatment discontinuation, and fatal events on study.

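### Crude rates of treatment-ending and fatal adverse events are expected to be too low, because counting starts at the first dose but patients enter only after it

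*SAP*

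**What the plan says.** **Counting window.** SAP 5.4 takes all adverse events "reported from Day 1 of study treatment to 30 days post last dose of study treatment". SAP 9.5.1 repeats this for the tables: "The descriptive summaries presenting treatment emergent AEs will include AEs reported from Day 1 of study treatment to 30 days post last dose". SAP 5.1 defines Day 1 as "the first day with trabectedin + PLD administration therapy". Protocol 8.2.2 and 10.4.5 use the same window.

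**Entry rule.** Protocol 4.3.1: "Patients must have received a minimum of 1 cycle of trabectedin + PLD before their inclusion in the study". Protocol 6 sets the earliest consent: "The ICF must be signed 1 or more days following completion of the initial trabectedin + PLD administration (1st treatment cycle"). No latest cycle for consent is given. Protocol 6.2: "The Observation Period will begin with the first trabectedin + PLD dose administered after the signing of the ICF". The notes to the schedule of events (Protocol 7, Table 1) place that dose at cycle 2 or later.

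**Denominator.** SAP 6.1 defines the FAS as "all the patients enrolled into the study and who have at least one administration of trabectedin" and uses it for safety.

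**Pre-consent data.** For patients enrolled later in treatment, Protocol 6.2.1 asks for information back to the first administration, where it is available. The same list words the safety item as applying at the visit. SAP 9.4.4 says that administration setting and dose modifications are not collected before consent and asks for footnotes on those tables. The adverse event tables carry no such footnote.

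**The concern.** The clock for adverse events starts before a patient can enter the study. A patient whose treatment ended through toxicity or death between the first dose and consent is not enrolled, so she is missing from both the event count and the denominator. Collecting earlier cycles retrospectively does not repair this, because it covers only patients who were later enrolled.

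Safety of the combination is a secondary objective. SAP 9.5.1 plans a summary of events leading to discontinuation and of fatal events, and SAP 9.2 plans deaths within 30 days of the last trabectedin dose. These are the events that the entry rule tends to remove. A reader comparing the crude FAS percentages with trials that followed every patient from the first dose would not be comparing like with like, and nothing in the tables would say so.

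**Working it through.** The documents give no figure on this point, so there is nothing to reproduce. The check asks what selection at entry does to a crude percentage.

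**Inputs**
- D, the rate among all who start treatment. For illustration, Protocol 1.1.3.2 cites 17% for discontinuation due to adverse events and 89% for grade 3-4 events with trabectedin + PLD.
- u, the share of starters lost before consent. Not in the documents; assumed 1% to 10%.
- e, the event rate among those lost. Not in the documents; assumed 0% to 100%.
- N = 300, the planned minimum (SAP 3.2).

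**Formula.** Observed rate among enrolled patients = (D − u·e) / (1 − u). It is below D only if e > D.

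**Discontinuation due to adverse events, D = 17%**

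| u | e = 0% | e = 17% | e = 50% | e = 100% |
|---|---|---|---|---|
| 1% | 17.2% | 17.0% | 16.7% | 16.2% |
| 3% | 17.5% | 17.0% | 16.0% | 14.4% |
| 5% | 17.9% | 17.0% | 15.3% | 12.6% |
| 10% | 18.9% | 17.0% | 13.3% | 7.8% |

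Example: (0.17 − 0.05 × 1) / 0.95 = 12.6%. That shift of 4.4 points compares with a 95% half-width at N = 300 of 1.96 × √(0.17 × 0.83 / 300) = 4.3 points.

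**Grade 3-4 events, D = 89%, u = 5%.** The observed rate is 88.4% at e = 100%, 90.0% at e = 70% and 91.1% at e = 50%. The effect is small and its sign depends on e.

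**When the direction reverses.** Suppose a share q of starters is lost for toxicity, all with the event, and a share r for other reasons, none with it. Then e = q / (q + r), and the observed rate exceeds D when r/q > (1 − D)/D. For D = 17% this is 0.83 / 0.17 = 4.88; for D = 89% it is 0.11 / 0.89 = 0.12. For discontinuations, losses for other reasons would have to outnumber toxicity losses almost five to one. For grade 3-4 events, about one to eight is enough.

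**What the plan does about it.** SAP 9.2 reports the number of cycles before consent and the time from first dose to consent, but does not link either to event rates. SAP 8.3 relies on the site log of non-participation, whose reasons are refusal, no reply and criteria not met; none identifies a patient who stopped or died before being invited. No delayed-entry analysis, split at consent or sensitivity analysis is planned, and SAP 10 declares no significant changes from the protocol.

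**The case against.** The strongest reply is that early toxicity is not shut out. Consent is possible one day after the first infusion, and SAP 6.1 asks for enrolment and one trabectedin administration, not a post-consent one. A patient who consents on the next day and stops before cycle 2 can be in the FAS, and Protocol 8.2.2 collects her events from the first dose. Early events of enrolled patients that did not end treatment are counted too. All of this stands, and it limits the point to events that ended treatment, or life, before consent.

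A reader might also infer more than the documents support:
- **That all safety percentages are too favourable.** This is not shown; the 89% example moves either way.
- **That pre-consent events are merely recalled while later ones are solicited.** Protocol 8.2 and SAP 9.5.1 describe one solicited system from the start of treatment. Availability limits apply in both periods (Protocol 6.2.1 and 6.2.2). Weaker early capture is plausible, but it is an inference.
- **That the antiangiogenic groups are biased differently.** This is possible if enrolment delay differs, but nothing in the documents shows it.
- **That the Day 1 window is wrong.** It matches the protocol. The difficulty lies in combining it with the entry rule, without a label or supplementary analysis.
- **That the loss can be computed from a constant hazard.** Spreading 17% over six cycles gives 1 − 0.83^(1/6) = 3.1% per cycle. But Protocol 5.1.1 sets no limit on cycles, consent can come one day into cycle 1, and the distribution of enrolment times is not given.

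It is also fair that the analysis is descriptive and that SAP 9.2 will make enrolment delay visible. That tells the reader that delay exists, but not what it does to the event tables.

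**Conclusion.** The point holds for a limited set of outputs. Crude FAS percentages for adverse events leading to discontinuation, fatal events and other early treatment-ending events are expected to be too low, because patients who died or stopped for toxicity before consent are absent. If 1% to 5% of starters were lost and all of them for toxicity, a 17% discontinuation rate would be observed as 16.2% to 12.6%. The upper end of that loss gives a bias about as large as the sampling error at N = 300. These figures are illustrations: neither the share lost nor its causes are in the documents, and no rate is available to size the effect on fatal events. For overall and grade 3-4 percentages the direction is not established.

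**What to change.** In SAP 9.5.1, with the table list in SAP 11.1 extended to match:

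1. Keep the Day 1 tables that Protocol 10.4.5 specifies. Footnote them as conditional on surviving on treatment to enrolment, and as including pre-consent events collected retrospectively when available.
2. Add supplementary tables that split adverse events, serious adverse events, adverse drug reactions, discontinuations due to adverse events and deaths by onset before or after consent.
3. Give post-consent incidence per cycle at risk, with each patient entering the risk set at the consent date. The Index date is not suitable: it is the first post-consent dose, so it would drop consented patients who stop before an on-study dose and leave events between consent and that dose without time at risk.
4. Flag onset dates that SAP 12.1 imputes to the first dose, since the rule places them before consent, and check how far the split depends on them.
5. State in SAP 6.1 that the FAS does not require a post-consent dose.

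The cost is a few extra tables and some SAP wording; the consent, cycle and onset dates are already needed for planned outputs. The split does not recover the missing patients, and post-consent rates are still conditional on reaching enrolment. It does make clear what each percentage estimates.

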6. ANALYSIS DATASETS

6.1 Full Analysis Set

The full analysis set (FAS) will consist of all the patients enrolled into the study and who have at least one administration of trabectedin. The FAS will be the primary analysis set for the safety analyses and analyses assessing effectiveness.

7. INTERIM ANALYSIS

An interim analysis after 50% (i.e., ~150 patients) of the recruitment will be performed in order to obtain a first approach of the results.

8. DATA SCREENING AND ACCEPTANCE

Edit checks to clean the data are to be described in the data validation plan as part of the data management plan (DMP). Data management (DM) for this study will provide clean raw data for the planned analysis (interim and final).

8.1 Data Handling and Electronic Transfer of Data

All data for this study will be received from data management as SAS datasets for the analysis and as described in the Data Transfer Plan.

Data coding will be applied as agreed:

Data type	Coded, Yes or No?
AEs	Yes
Prior Anticancer Therapy (Baseline Visit)	Yes
Medical History	No
Commeds	Yes
Surgery	No
Subsequent anticancer drugs	Yes

8.2 Handling of Missing and Incomplete Data

If dates are missing or incomplete for adverse events, concomitant medication data, deaths or prior anticancer therapies, algorithms as defined in Section 12.1 will be used. Dates of assessment for reported tumor response assessment are expected to be complete. If there are any missing or partial missing dates in this data field, the study statistician will be informed.

8.3 Detection of Bias

The reason for non-participation in the study (patient declined, no reply, patient not fulfilling the inclusion criteria, or presence of any exclusion criterion) will be recorded in a patient qualification log at each site. This will enable subsequent assessment of potential non-participation (selection) bias necessary for quality assurance of the data collected. Given the variation of clinical practice not only across, but also within countries, a good geographical representation of patients with relapsed ovarian cancer will be attempted

by targeting study centers spread across the regions of each of the countries. This variation in clinical practices will contribute to more representative results for each country as well as across this European region.

8.4 Distributional Characteristics

The assumptions behind each statistical method will be assessed. If the assumptions are not met, these will be described and further analyses may be carried out using data transformations and/or alternative analytical methods. The use of transformations or alternative methods will be fully described in the final study report.

9. STATISTICAL METHODS OF ANALYSIS

9.1 General Principles

All analysis will be based on the FAS and will be presented overall and by previous antiangiogenic usage (yes/no).

Appropriate descriptive statistics will be produced for each parameter. For continuous data the mean, standard deviation, median, minimum and maximum will be presented. For categorical data, the frequency and percentage in each category will be presented. The data will be analyzed using the normal approximation and its 95% CI. However, in analyses where sample size is considered to be too low, the exact binomial estimator and its 95% CI will be calculated. Time-to-event endpoints (PFS and OS) and their fixed-time estimations will be analyzed using the Kaplan-Meier (KM) method.

Any p-values presented will be descriptive in nature and the significance level selected will be 5%.

Statistical analyses will be conducted using SAS version 9.4 or later for Windows, and/or any other applicable software suitable for the planned statistical analyses.

9.2 Patient Accountability

A summary of the number and percentage of patients enrolled by country and site will be produced.

Data with reasons for non-participation in the study (patient declined, no reply, patient not fulfilling the inclusion criteria, or the presence of any exclusion criterion) collected and recorded in the patient qualification log at each site will be summarized upon data availability.

Patient disposition over the course of the study and summaries for inclusion/exclusion criteria will be provided. The disposition summaries will include the number of patients enrolled, number of patients who did not receive any trabectedin, and the number of patients included in the FAS. The number of trabectedin cycles received before IC was provided and for those patients, time from first dose of trabectedin to IC will be presented.

Reasons for treatment discontinuation will be summarized along with reasons for not completing the study as reported by the investigators.

Survival status at end of study, including number of deaths along with cause of death, will be summarized. Number of deaths along with cause of death within 30 days of last dose of trabectedin will also be presented.

9.3 Demographic and Baseline Characteristics

Summary statistics for each of the following demographic and baseline characteristics will be tabulated based on the FAS:

- Age as continuous and categorical : <65, [65, 75) and ≥ 75 years
- ECOG/WHO performance status
- BRCA-1/2 status
- Baseline weight, height, investigator reported BSA and derived BSA
- Time since initial ovarian cancer diagnosis, tumor grade and histology at initial tumor diagnosis
- Time since relapsed ovarian cancer diagnosis
- Prior tumor therapies, including surgery, and radiotherapy
- Occurrence of physical examination abnormalities and body systems in which abnormalities were found

- Anti-tumor treatment (chemo and non-chemo) including bevacizumab usage, PD reported during or after bevacizumab, number of regimens received, best response reported for the latest regimen received prior to trabectedin, time since latest regimen last dose taken, time since latest regimen reported PD and recurrence
- Medical history: co-morbidities
- Baseline imaging

9.4 Effectiveness Analyses

9.4.1 Analyses of Effectiveness Primary Endpoint

The primary endpoint for this study is PFS. Summaries of the primary endpoint will be based on the FAS. KM estimates and 95% CIs will be calculated based on estimated variance for log-log transformation of the estimate. KM time to event curves will also be presented.

9.4.2 Analyses of Effectiveness Secondary Endpoints

Objective Response

Objective response is defined as a best tumor response of complete or partial response as reported by the investigator in the overall response evaluation. Patients without an assessment of disease response will be treated as non-responders.

Descriptive statistics will be provided for best overall tumor response. The number and percentage of patients within each category of best response (CR, PR, SD, PD, and not evaluable (NE) (including reported in the electronic case report form (CRF) as not evaluable) and not done (including not assessed, not reported, and not done) will be presented. The proportion will be estimated by dividing the number of patients within each category of response by the number of patients available in the full analysis set. Each patient will be counted within only one response group, with the best response during the study (from the start of the treatment until the end of study treatment or PD, whichever occurs first), as reported by the investigator. No confirmation of response requirement will be applied for this analysis. Objective response rate (CR + PR) and two-sided exact binomial 95% confidence intervals will be presented. Additionally, descriptive

statistics for objective response will be presented stratified on BRCA 1/2 status (positive, negative, unknown).

Disease Control

The disease control will be reported along with two-sided exact binomial 95% confidence intervals.

Overall Survival

OS will be descriptively analyzed as done for the primary endpoint PFS.

9.4.3 Analyses of Effectiveness Other Endpoints

Symptomatic Response

Symptomatic response will be summarized for the treatment period including 30 days post last trabectedin administration.

9.4.4 Analyses of Other Endpoints

ECOG

ECOG/WHO performance status scores will be summarized at baseline, worst/best scores under treatment, and scores at end of treatment. The change in scores from baseline to best/worst and end of treatment scores will also be summarized presenting categories: <0 (indicating an improvement), 0-2, >2-4, and >4 (indicating worst deterioration).

Treatments

The recommended dosage for trabectedin in relapsed ovarian cancer is 1.1 mg/m² administered as a 3-hour infusion every 3 weeks (3h_q3w), immediately after infusion of 30 mg/m² PLD. There is no predefined limit as to the number of cycles of treatment with trabectedin. Treatment may continue as long as the treating physician feels there is benefit, even in the presence of apparent progression of disease. To minimize the risk of PLD infusion reactions, PLD infusion should be in accordance with the SmPC. Any

trabectedin dose modifications and/or change in dosing interval should be in accordance with the SmPC and the treating clinician's best clinical judgment.

Patients must receive corticosteroids (e.g., 20 mg dexamethasone iv) 30 minutes prior to PLD (in combination therapy) or Yondelis (in monotherapy); not only as anti-emetic prophylaxis, but also because it appears to provide hepatoprotective effects. Additional anti-emetics may be administered as needed.

1.

Trabectedin administration history will be summarized presenting the number of previous cycles received prior to IC. Descriptive statistics will be calculated for total number of cycles started or infusions received, trabectedin administration setting (inpatient/ outpatient), trabectedin administered dose per infusion (mg), cycle duration (days), trabectedin treatment duration will be presented as number of weeks on trabectedin treatment. Cumulative dose administered, dose intensity (mg)/week, relative weekly dose intensity (%), and total dose of trabectedin administered (mg) per cycles will also be presented. The number and percentage of patients with modifications (including dose missed, reductions, dose delays, or doses withheld) from the investigator reported schedule will be summarized by type of dose modification and reason for the dose modification. The number of dose missed/reductions/interruptions/delays per patient will also be summarized.

Data for trabectedin administration setting (inpatient/ outpatient) and dose modifications is not collected for drug taken prior to IC. For this reason summaries will include appropriate footnotes clarifying this.

Finally, proportion of patients treated with < 6 cycles and \geq 6 cycles stratified on BRCA 1/2 status (positive, negative, unknown), will also be quantified.

2.

PLD administration history will be summarized presenting the number of previous cycles received prior to IC. Descriptive statistics will be calculated for total number of cycles started or infusions received, PLD administration setting (inpatient/outpatient), PLD administered dose per infusion (mg), PLD treatment duration will be presented as number of weeks on PLD treatment. Cumulative dose administered, dose intensity (mg)

/week, relative weekly dose intensity (%), and total dose of PLD administered (mg) per cycles will also be presented. The number and percentage of patients with modifications (including dose missed, reductions, dose delays, or doses withheld) from the investigator reported schedule will be summarized by type of dose modification and reason for the dose modification. The number of dose missed/reductions/interruptions/delays per patient will also be summarized.

Data for PLD administration setting (inpatient/ outpatient) and dose modifications is not collected for drug taken prior to IC. For this reason summaries will include appropriate footnotes clarifying this.

Finally, proportion of patients treated with < 6 cycles and \geq 6 cycles stratified on BRCA 1/2 status (positive, negative, unknown), will also be quantified.

3.

Number of patients receiving trabectedin + PLD, trabectedin alone, and PLD alone will be summarized.

4.

Exposure to subsequent anticancer drugs will be described. Time from last dose of trabectedin to first anticancer treatment received, overall type of therapy, setting (single, combo) and number of cycles, and best response for the next anticancer therapy post trabectedin will be described.

